#### 5.10.4 Electrocardiograms

All subjects will have ECGs performed at screening. All ECGs will be performed after subject has been in supine position for at least 5 minutes.

In Part A ECGs will be performed at the following times: predose, 10 minutes postdose, 2, 4, 8, and 24 hours postdose, and at the end of the study.

In Part B, ECGs will be performed at the following times (relative to the first dose): predose, 10 minutes postdose, 2, 4, 8, and 24 hours postdose, Day 9 (prior to check-out), Day 14, and at the end of the study.

5.10.5 Chest X-Ray

All subjects will undergo chest X-rays (PA and lateral) at screening and on Day 11 of Part A and Day 9 of Part B. Additionally, subjects in Part B may undergo chest X-rays on Day 35 if clinically indicated, as determined by the Investigator.

5.10.6 PPD Test

*PPD*: A PPD skin test will be performed at screening to assess for exposure to tuberculosis. The test site will be evaluated 48 to 72 hours after placement.

5.10.7 Other

Subjects will be closely monitored during the confinement period in the research facility. Subjects will remain seated, except as otherwise required for study procedures or personal needs, for the first 4 hours after dosing. Should the need to move about occur during the first 4 hours after dose administration (or after the first dose in Part B), subjects may be escorted to such procedures or activities by research personnel as deemed medically necessary.

Following dose administration, each subject will be queried periodically about changes in their health. Responses will be transcribed in each subject's source documentation.

Subjects will be instructed to inform the study physician and/or research personnel of any AEs that occur at any time during the study.

Procedures will be completed as specified in this protocol unless contraindicated due to a reported AE.

Medical emergency personnel trained in advanced cardiac life support will be on site to monitor subjects during the confinement period in the research center. Emergency medical equipment including but not limited to intubation equipment, pulse oximetry, crash cart, and defibrillator shall be maintained on site to administer appropriate medical care should it be required. A physician will remain on site for a minimum of 4 hours after dose administration and will be available immediately by cell phone or pager thereafter.

Gossamer Bio, Inc.

#### 6 ADVERSE EVENTS

Subjects will be monitored for any AEs from the beginning of confinement until the end-of-study visit. The Investigator or a medically qualified designee will review each event. The Investigator or a Sub-Investigator will assess its relationship to the study drug. Each sign or symptom will be graded for severity, and the date and time of onset, cessation and resolution will be recorded. Treatment of any adverse reactions will be evaluated and managed by a physician, either at the study site or at a nearby hospital emergency room, as appropriate. All non-serious AEs will be reported on a regular basis or as specified by the Sponsor.

#### 6.1 Definitions

6.1.1 Adverse Event

An AE is defined as any untoward medical occurrence associated with the use of a drug in humans, whether or not considered drug related.

An AE can be any unfavorable and unintended sign (eg, an abnormal laboratory finding), symptom, or disease temporally associated with the use of a drug, without judgment to causality. An AE can arise from any use of the drug (eg, use in combinations with another drug) and from any route of administration, formulation, or dose, including an overdose.

6.1.2 Serious Adverse Event/Serious Suspected Adverse Reaction

A serious AE (SAE) or serious suspected adverse reaction, in the view of either the investigator or Sponsor, results in any of the following outcomes: Death, a life-threatening AE, inpatient hospitalization or prolongation of existing hospitalization, a persistent or significant incapacity or substantial disruption of the ability to conduct normal life functions, or a congenital anomaly/birth defect.

Important medical events that may not result in death, be life-threatening, or require hospitalization may be considered serious when, based upon appropriate medical judgment, they may jeopardize the patient or subject and may require medical or surgical intervention to prevent one of the outcomes listed in this definition.

6.1.3 Life-Threatening Adverse Event/Life-Threatening Suspected Adverse Reaction

A life-threatening AE/life-threatening suspected adverse reaction, in the view of either the Investigator or Sponsor, places the patient or subject at immediate risk of death. It does not include an adverse reaction that, had it occurred in a more severe form, might have caused death.

Gossamer Bio, Inc.

## 6.1.4 Unexpected Adverse Event/Unexpected Suspected Adverse Reaction

An unexpected AE/unexpected suspected adverse reaction is an AE or suspected adverse reaction that is not listed in the investigator brochure or is not listed at the specificity or severity that has been observed; or, if an investigator brochure is not required or available, is not consistent with the risk information described in the general investigational plan or elsewhere in the current application, as amended.

## 6.2 Serious Adverse Event Reporting

The Investigator or designee will notify the appropriate sponsor contact immediately after the SAE detection, observation, or report of occurrence (regardless of the relationship to test article). The sponsor contact information for SAE reporting is provided below:

[name] CEO Gossamer Bio, Inc. [name] [contact]-hour contact number: [contact] Email: [contact]

These SAE reports must contain the following information:

- A. Study name/number (for EU also the Eudract number)
- B. Study drug
- C. Investigator details (name, phone, fax, e-mail)
- D. Subject number
- E. Subject initials
- F. Subject demographics
- G. Clinical event
  - 1) Description
  - 2) Date of onset
  - 3) Treatment (drug, dose, dosage form)
  - 4) AE relationship to study drug
  - 5) Action taken regarding study drug in direct relationship to the AE
  - H. If the AE was fatal or life-threatening
- I. Cause of death (whether or not the death was related to study drug)
- J. Autopsy findings (if available)

Gossamer Bio, Inc.

Any new SAE that occurs within one month after the study period and is considered to be possibly related to the Investigational Medicinal Product (IMP) should be recorded and reported immediately to the Sponsor.

The person responsible for the study shall take care that the study has been carried out in accordance with pharmacovigilance local regulations.

All serious event reporting will adhere to 21 CFR 312.32 for IND drugs and 21 CFR 314.80 for marketed drugs (15-day alerts). The Institutional Review Board (IRB) will be notified of the alert reports per FDA regulations.

All AEs, including SAEs, will be followed to resolution when possible. All AEs and treatment administered will be recorded on the case report form (CRF).

The Sponsor will be responsible for reporting and processing any SAEs to the FDA or other applicable regulatory agency.

#### 6.3 Relationship to Study Treatment

The relationship between the AE and the investigational product will be determined by the Principal Investigator or Sub-Investigator on the basis of his/her clinical judgment and the following definitions:

#### **Related**:

The AE follows a reasonable temporal sequence from the study product administration, and cannot be reasonably explained by the subject's clinical state or other factors (e.g., disease under study, concurrent diseases, or concomitant medications).

The AE follows a reasonable temporal sequence from the study product administration, and represents a known reaction to the drug under study or other drugs in its class, or is predicted by the known pharmacological properties of the drug.

The AE resolves with discontinuation of the investigational product and/or recurs with rechallenge, if applicable.

#### **Possibly Related:**

An AE may be considered possibly related if or when (at least two of the following):

- It follows a reasonable temporal sequence from administration of the study product;
- It could not readily have been produced by the subject's clinical state, environmental or toxic factors, or other modes of therapy administered to the subject.
- It follows a known pattern of response to the study product.

## Not Related:

The AE does not follow a reasonable temporal sequence from study product administration, or can be reasonably explained by the subject's clinical state or other factors (e.g., disease under study, concurrent diseases, and concomitant medications).

## 6.4 Pregnancies

Any pregnancy will be considered a protocol violation. Pregnancies will not be documented or reported as AEs unless directed to do so by the Sponsor. However, if at any time the pregnancy falls under the scope and definition of an SAE, it will then be reported as such.

## 7 GENERAL CONSIDERATIONS

## 7.1 Basic Principles

This research will be carried out in accordance with the protocol, the International Council for Harmonisation of Technical Requirements for Pharmaceuticals for Human Use (ICH), Guideline for Good Clinical Practice: Consolidated Guidance (E6), and applicable regulatory requirements(s) including clinical research guidelines established by the Basic Principles defined in the U.S. 21 CFR Parts 50, 56, and 312 and the principles enunciated in the Declaration of Helsinki (revised version Fortaleza 2013).

## 7.2 Institutional Review Board

This protocol will be reviewed by an appropriate IRB and study enrollment will not commence until the Board has approved the protocol or a modification thereof. The Board is constituted and operates in accordance with the principles and requirements described in the U.S. Code of Federal Regulations (21 CFR Part 56).

## 7.3 Informed Consent

Written informed consent will be obtained from each subject prior to performing any baseline study-specific evaluations. The informed consent document is prepared by the Investigator or designee, subject to review and approval by the Sponsor, and forwarded to a qualified IRB for final review and approval. The IRB-approved document must contain, at minimum, the eight basic elements of informed consent. Only the most recently IRB-approved Informed Consent Document must be used to consent prospective study subjects. One copy of the signed and dated informed consent document will be given to the subject and the original retained by the Investigator/site.

#### 7.4 Indications for Subject Withdrawal

Subjects will be free to withdraw at any time for any reason, or they may be withdrawn if necessary, to protect their health and safety or the integrity of the study data.

Gossamer Bio, Inc.

The final report will include reasons for withdrawals. In the event of an early termination, subjects will undergo the procedures described in Section 5.9.

## 7.5 Termination of the Study

The Principal Investigator reserves the right to terminate the study in the interest of subject safety and welfare. The Sponsor reserves the right to terminate the study at any time for administrative reasons.

#### 7.6 Documentation

All documents pertaining to the study, including a copy of the approved protocol, copy of the informed consent document and Health Insurance Portability and Accountability Act (HIPAA) documents, completed CRFs (where applicable), drug accountability and retention records, and other study related documents will be retained in the permanent archives of the study site. These will be available for inspection at any time by the Sponsor or the FDA. Per 21 CFR 312, record retention for this study is required for a period of two years following the date on which this study agent is approved by the FDA for the marketing purposes that were the subject of this investigation; or, if no application is to be filed or if the application is not approved for such indication, until two years following the date on which the entire study (not merely the Investigator's portion of the study, if it involved more than one investigator) is completed, terminated, or discontinued, and the FDA is notified.

Subject records will be kept private except when ordered by law. The following individuals will have access to study subject records: Principal Investigator and designees, study Sponsor, monitors, and auditors, the FDA, other government offices, and the IRB.

## 7.7 Trial Monitoring

Sponsor personnel (or designees) will be responsible for monitoring the study to ensure compliance with the protocol and Good Clinical Practice (GCP). Compliance may be verified by one or more of the following methods: on-site visits, frequent communication with the Investigator, and/or review of CRFs and source documents. The Investigator agrees to permit such monitoring as well as audits or reviews by regulatory authorities and the IRB.

#### 7.8 Reimbursement, Indemnity, and Insurance

Reimbursement, indemnity, and insurance shall be addressed in a separate agreement on terms agreed upon by the parties.

## 8 PHARMACOKINETIC ANALYSIS

#### 8.1 Analytical Methodology

Plasma and urine samples will be analyzed for PK10571 using validated assays. The samples from all evaluable subjects who complete their study period will be analyzed.

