### **3 STUDY DESIGN SUMMARY**

This is a first-in-human, single-center, randomized, double-blind, placebo-controlled, two-part study in healthy adult males and females of non-childbearing potential. Because the safety profile of PK10571 in humans is unknown and this is the first clinical study to assess PK10571 in humans, a single-ascending dose escalation design will be used in Part A of the study. Part B will be a multiple-ascending dose escalation design, to be run only after review of safety and pharmacokinetic data from Part A.

In the single ascending dose study (Part A) at least 4 dose levels of PK10571 will be tested:

An optional fifth dose level of up to may be added, based on safety and pharmacokinetic data from the first 4 cohorts. Subjects will be randomized into one dose cohort and receive either PK10571 or placebo. Within each cohort, 6 subjects will receive active drug and 2 subjects will receive placebo.

In the multiple ascending dose study (Part B), up to three dose levels of PK10571 will be tested. The daily dose will be administered daily for 7 days with close clinical monitoring. The dose for the first cohort of Part B will be determined by review of the safety and pharmacokinetic data from Part A by the Safety Review Committee. The dose interval for the first cohort of Part B (i.e., once daily, twice daily, or up to three times daily) will be determined by review of the safety and pharmacokinetic data from Part A by the Safety Review committee. Subsequent doses and dosing intervals will be determined by review of the safety and pharmacokinetic data from the prior cohort.

For both Part A and Part B, for each cohort, randomization will occur in 2 blocks as follows: In the first block, 2 subjects (sentinel subjects) will be randomized 1:1 to receive PK10571 or placebo; in the second block, 6 subjects will be randomized 5 PK10571: 1 placebo. If PK10571 is well-tolerated in the sentinel subjects, the remainder of the cohort (n = 6) will be randomized. There will be a minimum of 48 hours between dosing of the 2 sentinel subjects and the remainder of the cohort.

The safety, tolerability, and pharmacokinetics of PK10571 will be evaluated in each sequential cohort prior to each dose cohort escalation, assessing the totality of all the safety data prior to initiating the next cohort.

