### 3.1 Part A

Part A of the study is a single ascending dose study design. Up to 5 dose levels will be studied. Subjects will receive either PK10571

placebo. Part A will enroll up to 40 subjects; 8 subjects per cohort. The data from each cohort will be analyzed before deciding whether to proceed with the next cohort.

Each cohort will include a sentinel group of 2 subjects (1 active and 1 placebo) who will be dosed at least 48 hours before the remaining subjects (5 active and 1 placebo). Dosing of the remaining subjects will occur following a safety evaluation of the sentinel group.

Gossamer Bio, Inc.

CONFIDENTIAL

or

Subjects will receive one of the treatments listed in Table 1. Within each cohort, subjects will be assigned to either active treatment or placebo in randomized fashion.

| Tuble 2 Tute A. Thunked Doses for Conditis 1, 2, and 5  |   |        |               |  |
|---|---|--------|---------------|--|
| Cohort  | Test Formulation Dose   |        | Placebo       |  |
| 1 - starting dose   | PK10571   | (n=6)* | Placebo (n=2) |  |
| 2 - second dose   | PK10571   | (n=6)* | Placebo (n=2) |  |
| 3 - third dose  | PK10571   | (n=6)* | Placebo (n=2) |  |
| 4 – fourth dose   | PK10571 up to   | (n=6)¶ | Placebo (n=2) |  |
| 5 – fifth dose  | PK10571 up to   | (n=6)p | Placebo (n=2) |  |
| FPD = fine particle do  | se; $n =$ number of subjects  |        |               |  |
| * Capsules with a nominal fill weight of the will be administered sequentially to achieve the target FPD for Doses 1-3. |   |        |               |  |
| " I  | Capsules with a nominal fill weight of weight will be administered to achieve the dose for cohort 4 (nominal 18 mg FPD (5 capsules) |        |               |  |
| P The capsule fill weight, FPD, and number of capsules to be administered will be determined to achieve the             |   |        |               |  |

Table 2Part A: Planned Doses for Cohorts 1, 2, and 3

P The capsule fill weight, FPD, and number of capsules to be administered will be determined to achieve the target dose for cohort 5, if the Safety Review Committee decides to proceed with this dose.

Each dose will be administered using an oral inhalation device following a 10-hour overnight fast. After dosing, no food will be allowed until 4 hours postdose. Meals will be standard and scheduled at approximately the same times relative to dose for each cohort.

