### 3.3 Safety Review Team

A Safety Review Committee consisting of the Principal Investigator or designee (e.g., a medically qualified sub-investigator) and Sponsor representatives with appropriate expertise will meet and review, at minimum, the 24-hour safety data for the sentinel group of each cohort in Part A prior to dosing the remainder of the cohort.

The Safety Review Committee will review the safety and pharmacokinetic data from each cohort in Part A. Dose escalation to the next level will occur only after review of the 24-hour pharmacokinetic data, and safety data up to and including Day 11 from the preceding cohort(s). The factors to be used in determining the next incremental dose are described in Section 3.4. There will be at least 2 weeks between dosing of each cohort.

The Safety Review Committee will review the safety and pharmacokinetic data of Part A before starting Part B. The pharmacokinetic data from the first 24 hours of Part B, Cohort 1 up to and including Day 7, and the safety data up to and including Day 14 will be reviewed prior to dosing of Part B, Cohort 2.

All available safety data will be assessed prior to each dose escalation, including but not limited to the following:

- All adverse events (AEs)
- Safety laboratory tests (i.e., hematology, chemistry and urinalysis)
- Coagulation tests
- Vital signs
- Physical examinations
- ECGs (12-lead)
- Pulmonary function tests (spirometry)

If the initial dose administered to Cohort 1 is not tolerated, a lower dose cohort may be allowed.

In subsequent cohorts, the dose may be decreased from the planned dose depending on results of safety and pharmacokinetic data.

Gossamer Bio, Inc.

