#### 8.2 Pharmacokinetic Analysis

Pharmacokinetic parameters for PK10571will be calculated using non-compartmental analysis. The following pharmacokinetic parameters will be determined:

The maximum plasma concentration ( $C_{max}$ ) and time to  $C_{max}$  ( $T_{max}$ ) will be taken directly from the data. The elimination rate constant,  $\lambda_z$ , will be calculated as the negative of the slope of the terminal log-linear segment of the plasma concentrationtime curve; the range of data to be used will be determined by visual inspection of a semi-logarithmic plot of concentration vs. time. Elimination half-life ( $T_{1/2}$ ) will be calculated according to the following equation:

 $T_{\frac{1}{2}} = 0.693 / \lambda_Z$ 

Area under the curve to the final sample with a concentration greater than the limit of quantitation (LOQ), (AUClast), will be calculated using the log trapezoidal method and extrapolated to infinity using:

 $AUC_{inf} = AUC_{last} + C_{last} / \lambda_Z$ 

where  $C_{last}$  is the final concentration  $\geq LOQ$ .

All evaluable subjects will be included in the pharmacokinetic analysis. Pharmacokinetic calculations will be performed using appropriate software, e.g. PhoenixTM WinNonlin® (Version 6.3 or higher, Pharsight Corporation) and/or SAS® (Version 9.3 or higher, SAS Institute Inc.).

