6.1.2. PK Population

The PK population is defined as all subjects who received active study drug and have at least one quantifiable postdose concentration.

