8. CHANGES TO PLANNED PROTOCOL ANALYSIS

No changes planned to protocol analysis.

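### Protocol 8.1 ties assay to evaluable completers, with neither term defined, while the SAP PK population has no completion condition, so early withdrawals' exposure data could be lost

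*Protocol*

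**What the plan says.** Three rules bear on whose concentrations are used.

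- **Protocol 8.1 (Analytical Methodology):** "The samples from all evaluable subjects who complete their study period will be analyzed". This is the protocol's only statement of whose samples are assayed.
- **Protocol 8.2 (Pharmacokinetic Analysis):** "All evaluable subjects will be included in the pharmacokinetic analysis". Completion is not mentioned here.
- **SAP 6.1.2 (PK Population):** "all subjects who received active study drug and have at least one quantifiable postdose concentration".

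SAP Section 8 reads "No changes planned to protocol analysis". The SAP was written against protocol version 5.0; the summary of changes to version 5.3 (Protocol Appendix 6) lists nothing in Section 8.

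The protocol also depends on PK between cohorts. For Part A, Section 3.3 says: "Dose escalation to the next level will occur only after review of the 24-hour pharmacokinetic data", together with safety data through Day 11. For Part B, it requires Cohort 1 PK up to Day 7 and safety up to Day 14 before Cohort 2 is dosed. Section 3.4 lists Cmax and AUC among the factors for choosing the next dose. End of study is Day 11 in Part A and Day 35 in Part B (Section 5.9). Withdrawn subjects may be replaced on the same treatment, at discretion (Section 3).

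**The concern.** Completion is known only after dosing. A rule that assays completers therefore selects subjects on a post-dose outcome, in cohorts where "Within each cohort, 6 subjects will receive active drug and 2 subjects will receive placebo". The SAP's wider definition does not repair this, because a subject whose samples were never assayed cannot show a quantifiable concentration. A laboratory working from 8.1 and a statistician working from SAP 6.1.2 would expect different sets of subjects.

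At stake is the exposure record of someone who leaves early. If the reason is intolerance linked to high exposure, the cohort summary is understated, and the exposure value that belongs with the adverse event is never measured. This is a first-in-human study, so that pairing is of particular interest.

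**Working it through.** **1. The plan's own figures.** Part A: 5 cohorts × 8 = 40. Part B: 3 cohorts × 8 = 24. Both reproduce the stated enrolment, with 5 × 6 = 30 and 3 × 6 = 18 on active drug. Section 5.1 says the sample size has no statistical basis. The documents give no withdrawal rate and no between-subject CV, so every CV and rate below is an assumption.

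**2. The two rules applied to the same subject.**

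| Subject on active drug | Protocol 8.1 as written | SAP 6.1.2 |
|---|---|---|
| Completes, has a quantifiable value | Assayed | Included |
| Part B, withdraws on Day 4 with a full Day 1 profile | Not provided for | Included, but only if assayed |
| Part A, lost on Days 4–10 with all 14 PK samples taken by 48 hours | Not provided for if the period ends on Day 11; assayed if it ends at 48 hours | Included, but only if assayed |

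**3. Timing in Part B.** The review before Cohort 2 needs safety data only to Day 14. It can therefore fall up to 35 − 14 = 21 days before Cohort 1 reaches end of study, when completion is not yet known. PK to Day 7 has to be assayed anyway.

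**4. Effect of losing one of six.** Let r be the lost subject's exposure divided by the geometric mean (GM) of the other five. Then GM(6) = GM(5) × r^(1/6), so GM(5)/GM(6) = r^(−1/6).

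| r (assumed) | 0.5 | 1 | 1.5 | 2 | 3 |
|---|---|---|---|---|---|
| GM(5)/GM(6) | 1.12 | 1.00 | 0.94 | 0.89 | 0.83 |

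**5. Conditional worst case: the highest exposure is lost.** Exposure is taken as log-normal with s = √ln(1 + CV²). In 400,000 simulated cohorts of six, the GM ratios (averaged on the log scale) were:

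| Assumed CV | 20% | 30% | 50% | 70% |
|---|---|---|---|---|
| Highest lost | 0.951 | 0.928 | 0.887 | 0.852 |
| Two highest lost | 0.910 | 0.869 | 0.798 | 0.740 |

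For one loss at CVs of 30%, 50% and 70%, the falls are about 7%, 11% and 15%.

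**6. Withdrawal unrelated to exposure.** The simulated ratio is 1.00; only precision suffers. The 95% CI factor around the GM is exp(t × s/√n). At CV 50% it widens from 1.64 (n = 6) to 1.80 (n = 5).

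**7. How often the question arises.** The chance of at least one withdrawal among six is 1 − (1 − p)^6. At assumed rates p of 2%, 5% and 10% it is 11%, 26% and 47%.

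**8. Where the effect falls.** It falls on Part A summaries and dose proportionality, and on Part B Day 1 summaries and Day 1 dose proportionality. The Day 7 versus Day 1 ANOVA (SAP 6.11) has a subject factor, so someone without Day 7 data adds nothing to that contrast under either rule. A Part B subject who leaves after Day 7 has given both profiles. Section 8.1 would miss that subject only on the Day 35 reading, which step 3 shows does not fit the interim review.

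**The case against.** The best defence is that 8.1 is loosely worded rather than restrictive.

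- **It does not say *only*.** It provides for completers and is silent on everyone else; 8.2 then takes all evaluable subjects. A reader might infer an express bar on assaying withdrawals, and the text does not contain one. What stands is that no other sentence provides for those samples, so exclusion is the natural reading of the completion clause.
- **The period may be short.** Appendix 1 counts sampling time points per period, 14 in Part A. On that usage a Part A subject completes at 48 hours, while still confined, and a loss on Days 4–10 does no harm. This is a fair reading of an undefined term. In Part B, however, the scheduled samples themselves run to Day 35.
- **Part A is a single dose.** There is no later dosing to stop, so loss there requires leaving the study within 48 hours or the longer reading of the period. That makes the problem less likely, not impossible.
- **The SAP is already inclusive, and 8.1 concerns bioanalysis.** True, and the SAP's statement of no change may not have been aimed at 8.1. But an inclusive analysis set cannot use concentrations that were never measured.
- **Replacement restores the count.** It does, when used. It does not undo selection or recover the withdrawn subject's exposure.

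Two stronger inferences fail. One is that the Part B escalation review would lose profiles under a Day 35 rule: that review precedes Day 35, so such a rule cannot operate in it. The other is that cohort exposure would necessarily be biased: that takes a withdrawal, no assay of the samples, and a link between withdrawal and exposure.

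**Conclusion.** The mismatch holds on the text. Protocol 8.1 provides for assay of evaluable completers, SAP 6.1.2 has no completion condition, neither protocol term is defined, and the SAP declares no change. Followed as written, 8.1 leaves withdrawals outside the SAP PK population through lack of assay.

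The consequence is conditional. One unreplaced loss removes one of six active profiles (17%) and costs precision. Exposure is understated only if withdrawal goes with high exposure. The 7%, 11% and 15% figures rest on assumed CVs and on the single highest subject being the one lost and not assayed, so they are the worst case for one loss and not an expected bias. If the lost subject had half the others' exposure, the GM would be overstated by 12%. The documents give no withdrawal rate, CV or exposure–event relation from which to choose among these cases.

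Correction is still worthwhile: the stated rule can only discard information, and the samples concerned already exist.

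**What to change.** Make three changes.

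1. Replace the 8.1 sentence with: *Samples collected from all subjects who received active drug will be assayed, whether or not they complete the study.* The laboratory is already unblinded (Section 5.2.1), so it can apply this. Handling of placebo samples is a separate choice and can be stated alongside.
2. In 8.2, define *evaluable* as the PK population of SAP 6.1.2. The reference to the study period then drops out.
3. Add to the SAP that an incomplete profile contributes the parameters it supports; for example, a complete Day 1 profile supplies Day 1 Cmax and AUC0–24 even if Day 7 is missing.

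The cost is a few sentences and a few extra assays on samples already drawn, with no new blood sampling and no change to enrolment. With all six active subjects kept, the ratio in the working is 1.00 by construction.
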